14.10 Reporting of SAEs

14.10.1 Principal investigator

If an SAE occurs during the period from the start of study drug administration to Day 14, the investigators will take the necessary measures with the highest priority given to the safety of the subject, regardless of whether it is related to the study drug or not. The principal investigator will report the event to the sponsor. However, if the event is an SAE and related to the study drug, the event that have occurred until Day 28 will be reported to the sponsor in the same manner even after completion of the above-mentioned period.

The procedures are outlined below.

- (1) The sponsor should be informed of the occurrence of an SAE within 24 hours of acknowledgment of the occurrence (A form of “Report on serious adverse event (initial announcement)” shall be used, whenever possible). In addition, the SAE should be immediately reported to the head of the medical institution.

- (2) A form of “Report on serious adverse event” shall be prepared and reported to the sponsor and the head of the medical institution at the earliest possible time within 7 days after the first announcement has been submitted to the sponsor, and a copy of the report will be retained.
- (3) The investigators shall make efforts to collect more detailed information, and report it to the sponsor and the head of the medical institution if new information becomes available.

Emergency Contact (Sponsor)

Nobel Pharma Co., Ltd. Research and Development Division [name] [contact]、[contact] Night and holiday : [REDACTED] [REDACTED]

14.10.2 Sponsor

The sponsor shall follow the following procedures when the occurrence of an SAE has been reported by the investigators.

- (1) “Report on serious adverse event” shall be obtained at the earliest possible time within 7 days after the first announcement has been received from the investigators.
- (2) The sponsor will check details of the “Report on serious adverse event”, and refer to the investigators as appropriate if any additional information is considered necessary.
- (3) If the report is judged to meet the requirements of Article 273 of the Enforcement Regulations of the Pharmaceuticals and Medical Devices Act, the sponsor should report the SAE to the regulatory authorities within the specified period. In addition, the sponsor will report the relevant SAE in writing to each principal investigator and the head of each medical institution.

15 Criteria for Discontinuation of Study, Subject and Study Drug

15.1 Study drug discontinuation

If the subject meets any of the following criteria at any time before the second dose on Day 5, study drug administration for the subject shall be discontinued.

- (1) The subject has started to use invasive ventilator or ECMO.
- (2) The WBC count of the subject exceeds 25,000/ μ L.
- (3) An AE has occurred and the investigators judged it difficult to continue study drug administration.
- (4) The subject was found to be pregnant or suspected to be pregnant, or the subject wished to be pregnant or breastfeeding.
- (5) The subject was discharged from the hospital (including transfer to another hospital) and cannot continue to receive the study drug.

[Rationale]

- (1) It was set because accurate specified dose of the study drug is thought difficult.
- (2) and (3) It was set in order to ensure the safety of the subject.
- (4) It was set because the safety of sargramostim administration during pregnancy or lactation has not been established.
- (5) The possibility of discontinuation due to inevitable accident was considered.

Discontinuation of study drug administration does not necessarily preclude discontinuation of participation of the subject in the clinical study, and a policy was decided to follow-up and to collect the data on Japanese COVID-19 patients who participated in the clinical study whenever possible.

If an event meets the criteria for study drug discontinuation, the investigators shall follow the following procedures.

- The investigators shall immediately discontinue the study drug administration for the subject and perform observations/examinations at the time of discontinuation within 1 day of the discontinuation of study drug administration.
- If the event does not meet the criteria of “15.2 Withdrawal of subject from the study” and the observations/examinations can be performed, the subject will continue to participate in the study and continue the scheduled study procedures other than the administration of the study drug.
- The date and reason for discontinuation of study drug administration, as well as comments on discontinuation as appropriate, will be entered in the eCRF.

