10.3 Administration of study drug

Administration of study drug will start in the morning of Day 1 (twice daily, in the morning and evening between Day 1 and Day 5).

In the active treatment group, 250 µg/vial of sargramostim will be dissolved in 4 mL of physiological saline, and 2 mL of which will be administered twice daily (in the morning and evening) using an inhaler for 5 days, in principle (up to 10 days). In the control group, 2 mL of physiological saline will be administered twice daily (in the morning and evening) using an inhaler for 5 days, in principle (up to 10 days).

Approximately 10-15 minutes will be taken for one inhalation administration which shall be continue until the prepared solution has been depleted. During the inhalation administration, air cleaner or similar will be available for prevention against infection for healthcare workers and other patients.

The start date and time of the study drug administration should be recorded in the eCRF. Details of the preparation and dispensing of the study drug should be in accordance with the procedures specified separately.

All subjects may continue to receive inhalation administration of the study drug at the discretion of the investigators for up to Day 10 from Day 6 onward. After Day 6, the dosage and administration should be the same as that in the first 5 days.

Occurrence of serious allergic or anaphylactic reactions after administration of sargramostim has been reported. If a serious allergic or anaphylactic reaction occurs, administration should be discontinued and appropriate therapy should be initiated. The investigators shall follow up at least 1 hour after inhalation administration to ensure that no clinical symptoms such as acute hypersensitivity reactions (e.g., facial or extremity swelling, cough, urticaria, decreased consciousness, respiratory distress) are observed.

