13.6 Laboratory tests (blood chemistry, hematology, urinalysis, and pregnancy test)

The following items will be measured at the medical institution. If the measurement results deviate from the reference value, the investigators will assess whether the deviation is clinically significant. Pregnancy test will be performed only for women of childbearing potential. Pregnancy test will not necessarily be required for a female subject considered unable to become pregnant due to the following reasons: menopause (amenorrhea for at least 12 months without medical reasons), total hysterectomy, or that she does not get the first menstruation yet. The date of the sample collection and the test results will be entered in the eCRF.

Abnormal changes in laboratory test values that are judged by the investigators to be applicable to adverse events will be reported separately as adverse events (see "14.1 Definitions of AE").

Table 13.6-1 List of Laboratory Parameters

Hematology	Red blood cells count, white blood cells count, differential white leucocytes (neutrophils, lymphocytes, monocytes, eosinophils, basophils), platelets count, hemoglobin, hematocrit
Blood chemistry	Total protein, albumin, AST (GOT), ALT (GPT), γ -GTP, ALP, LDH, CK (CPK), total bilirubin, total cholesterol, HDL-cholesterol, LDL-cholesterol, triglycerides (TG), BUN, creatinine, blood glucose, Ca, Na, K, P, Cl
Urinalysis	Occult blood, protein, glucose, urobilinogen
Pregnancy test	Urine hCG or serum hCG

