14.1 Definition of AE

An AE is any unfavorable or unintended sign (including abnormal laboratory changes), symptom, or disease occurring in an assigned subject from the start of study drug administration, whether or not related to the study drug. Events occurring before the start of study drug administration will be treated as a current medical condition in this study.

AEs required to be entered in the eCRF will be those occurring from the start of study drug administration to Day 14 in this study. SAEs related to the study drug should be collected until Day 28.

Moreover, the subject's current medical condition is not considered an AE unless the severity worsens or the incidence increases after study drug administration. If the investigators judge that the change in a laboratory test value is an unfavorable event for the subject, the event will be assessed as an AE.

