14.8 Observation of AEs

The investigators shall observe the occurrence of AEs carefully through medical interview, medical examination, etc. from the start of study drug administration. If any AE is observed, appropriate measures should be taken, and the AE shall be followed up by the investigators until the AE disappears

or resolves as far as possible. However, if the investigators judge that further follow-up observation is not necessary and discontinue follow-up observation, or if the subject refuses it, the reason shall be entered in the eCRF.

For any AEs that have occurred, information of the name of the event, date and time of onset (or date and time when the event was found), severity, seriousness (serious/non-serious), action taken with the study drug (if yes, its contents), treatment for the event (yes or no), outcome, date and time of outcome (when the event disappeared, the date and time of disappearance), and causality to the study drug should be entered in detail in the eCRF.

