15.2 Withdrawal of a subject from the study

A subject who meets any of the following criteria shall be withdrawn from study participation.

- (1) The subject was found not to meet the inclusion criteria or to meet the exclusion criteria and to be ineligible for the clinical study according to the results of medical examinations, etc. performed after start of the clinical study.
- (2) The subject or the legally acceptable representative has requested to terminate the clinical study or to withdraw his/her consent.
- (3) The subject was dead.
- (4) The investigators judged that continuation of the clinical study is not desirable for the subject due to other reasons.

[Rationale]

- (1) It was set as a general item to ensure safety of the subject and to properly evaluate the study.
- (2) It was set in accordance with the principles of the Declaration of Helsinki and the GCP.
- (3) Since continuous observation cannot be performed, it was set as a discontinuation criterion due to inevitable accident.
- (4) In addition to above mentioned criteria, it was set as a general item for discontinuation criteria so that the investigators can judge appropriateness to continue the clinical study.

If an event occurs to meet the criteria for withdrawal of subjects from the study, the investigators shall follow the following procedures.

- The date of discontinuation (the date on which discontinuation was judged and the date of last dose, if possible) and the reason for discontinuation, as well as comments on discontinuation if necessary, will be entered in the eCRF.

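### The fixed WBC stop in Protocol 15.1 lapses at the second dose on Day 5, although 10.3 allows full dosing to Day 10; a count first found high after that dose triggers only judgement-based duties

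*Protocol*

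**What the plan says.** Protocol 15.1 lists five criteria for stopping study drug. All five fall under one lead-in: dosing must stop if the subject "meets any of the following criteria at any time before the second dose on Day 5". Criterion (2) reads "The WBC count of the subject exceeds 25,000" (per µL). The rationale in 15.1 gives subject safety as the reason for criteria (2) and (3).

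Protocol 10.3 then provides for longer dosing. All subjects "may continue to receive inhalation administration of the study drug at the discretion of the investigators for up to Day 10", and in that period "the dosage and administration should be the same as that in the first 5 days".

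Some laboratory and adverse-event duties have no Day 5 limit:

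- Section 13.6: "If the measurement results deviate from the reference value, the investigators will assess whether the deviation is clinically significant".
- Section 14.1: a laboratory change is assessed as an AE on this condition: "If the investigators judge that the change in a laboratory test value is an unfavorable event for the subject".
- Section 14.8: "If any AE is observed, appropriate measures should be taken".
- Section 14.10.1: for any SAE up to Day 14, the investigators take the necessary measures, putting subject safety first.
- Section 15.2(4): the subject is withdrawn if "The investigators judged that continuation of the clinical study is not desirable for the subject due to other reasons".

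Scheduled haematology is on Day 0, Day 5 and at discontinuation or exit. For a subject whose last dose is not on Day 5, the exit test is on the day of the last dose (Protocol Section 2, footnote 6; SAP 2.1.2.11.2).

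**The concern.** The sponsor chose a numeric WBC limit to protect subjects. It also excludes patients with diseases that cause leukocytosis, because it sees a higher safety risk from the drug in them (7.2, rationale 9). Section 4.1 describes GM-CSF as promoting differentiation into neutrophils and monocytes/macrophages, so a rising WBC is linked to the mechanism. The protocol does not say why the limit should end on Day 5 while the dose continues unchanged. As written, a subject whose count first passes 25,000/µL in a sample taken after the second Day 5 dose can go on receiving full doses to Day 10 without a breach of 15.1. What is at stake is subject safety in the extension.

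**Working it through.** **Which stops lapse.** The table compares 15.1 with the rest of the protocol.

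| Trigger | In 15.1, up to the second Day 5 dose | Fixed stop elsewhere without that limit |
|---|---|---|
| Invasive ventilator or ECMO | criterion (1) | Synopsis; Section 11 |
| WBC above 25,000/µL | criterion (2) | none |
| AE judged to make continuing difficult | criterion (3) | none |
| Known or suspected pregnancy | criterion (4) | 14.9 |
| Discharge, cannot continue dosing | criterion (5) | none (practical, not a safety limit) |
| Serious allergic or anaphylactic reaction | not named | 10.3 |

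The WBC threshold appears nowhere else. Withdrawal under 15.2(1) does not replace it: exclusion (9) concerns an underlying disease and, like the other exclusions, is judged at screening.

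**Which counts fall in the gap.** Dosing starts on the morning of Day 1, two doses a day, so the second Day 5 dose is dose 2 × 5 = 10.

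- Sample drawn before dose 10 and above 25,000/µL: the criterion is met in time. Dosing must stop at once, and the subject continues study procedures without drug. Days 6 to 10 are barred. This takes the criterion as met when the sample is drawn, not when the result is read.
- Sample drawn after dose 10, or on Days 6 to 10, and above the threshold for the first time: 15.1 does not apply. Only 13.6, 14.1, 14.8, 14.10.1 and 15.2(4) remain.

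**How much dosing is involved.** For last dosing day d, total doses are 2d and doses after the fixed stop has ended are 2(d − 5).

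| Last dosing day | Doses outside / total | Share |
|---|---|---|
| 5 | 0 / 10 | 0% |
| 6 | 2 / 12 | 17% |
| 7 | 4 / 14 | 29% |
| 8 | 6 / 16 | 38% |
| 9 | 8 / 18 | 44% |
| 10 | 10 / 20 | 50% |

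At 125 µg per dose, the maximum is 10 × 125 = 1,250 µg of 20 × 125 = 2,500 µg. This is worst-case exposure, not a measure of harm.

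**What is monitored.** The mandatory period contains one scheduled on-treatment WBC if the Day 5 sample precedes dose 10, and none if it is drawn later. No count is scheduled between the Day 5 sample and the day of the last dose. The schedule also seems to allow the Day 5 laboratory tests one extra day, since footnote 7 exempts only the two daily scales from the window. If so, a Day 6 sample could follow up to two extension doses (11 and 12). The extracted table is partly broken and its rows do not line up: the dosing row shows six filled marks for a five-day course. The extra day is therefore plausible, not established, and the gap does not depend on it.

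**Safety experience cited.** Section 4.3 reports 125 µg twice daily for 7 days (2 × 7 × 125 = 1,750 µg per cycle) and 8 days (2,000 µg per cycle) without safety concerns. In the melanoma study, 500 to 2,000 µg twice daily for 7 days (7,000 to 28,000 µg per cycle) did not reach the maximum tolerated dose.

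**The case against.** The strongest reply is that the Day 5 boundary is deliberate. Five days is the default course, so 15.1 sets out when that default must be overridden. From Day 6 there is no default to dose: the investigator has to choose to continue, can decline, may order extra tests (Section 13), and keeps the assessment, AE and withdrawal duties. The limit covers all five criteria, so WBC was not singled out. The inhaled experience in 4.3 is reassuring.

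Much of this stands. A reader might infer that safety oversight stops after Day 5; the sections listed above show that it does not. A reader might also infer that any subject with a high Day 5 count can be extended; 15.1 already forbids this when the sample precedes the second dose. The documents show no harm either, and the safety data limit the severity.

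The argument does not explain why a fixed threshold should give way to judgement while full-dose exposure continues. Every remaining safeguard is discretionary, and a fixed threshold exists to bound discretion. The cited courses at this dose were 7 or 8 consecutive days in another disease, and the melanoma dosing was in alternate weeks. In the COVID-19 study cited in 6.3, treatment after the fifth day was intravenous. None covers 10 consecutive inhaled days at this dose in COVID-19.

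**Conclusion.** The gap in the text is clear, and confidence in that part is high. The fixed WBC stop does not reach counts first above 25,000/µL in samples drawn after the second Day 5 dose, and no other section closes the gap. The AE criterion in 15.1(3) has the same time limit, but it rests on judgement in any case.

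The practical size is uncertain. Up to doses 11 to 20 are affected in a subject dosed to Day 10, and none in a subject who stops on Day 5. The number of active subjects extended could be anywhere from 0 to all 40 planned, and the frequency of such counts is not given. The Investigator's Brochure and separate procedures were not available; either might add a rule. The issue is subject safety only, with no effect on the primary analysis. It is a cheap improvement of modest severity.

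**What to change.** 1. In 15.1, replace the time limit in the lead-in with: at any time during study drug administration (up to Day 10).
2. In 10.3, require for any subject to be extended that the scheduled Day 5 WBC result be available and at or below 25,000/µL before the first Day 6 dose.

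The second change brings most of the practical gain, because it covers Day 5 samples drawn after the evening dose and rules out a Day 6 sample taken after extension doses. The first gives a fixed response to any unscheduled count in the extension. It does not by itself monitor Days 6 to 10, since the next scheduled count is on the day of the last dose.

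The cost is a wording amendment to two sections. Possibly a few more subjects stop early, and sites need the Day 5 result before dose 11. No visit or test is added, and the sample size does not change.

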15.2 Withdrawal of a subject from the study

A subject who meets any of the following criteria shall be withdrawn from study participation.

- (1) The subject was found not to meet the inclusion criteria or to meet the exclusion criteria and to be ineligible for the clinical study according to the results of medical examinations, etc. performed after start of the clinical study.
- (2) The subject or the legally acceptable representative has requested to terminate the clinical study or to withdraw his/her consent.
- (3) The subject was dead.
- (4) The investigators judged that continuation of the clinical study is not desirable for the subject due to other reasons.

[Rationale]

- (1) It was set as a general item to ensure safety of the subject and to properly evaluate the study.
- (2) It was set in accordance with the principles of the Declaration of Helsinki and the GCP.
- (3) Since continuous observation cannot be performed, it was set as a discontinuation criterion due to inevitable accident.
- (4) In addition to above mentioned criteria, it was set as a general item for discontinuation criteria so that the investigators can judge appropriateness to continue the clinical study.

If an event occurs to meet the criteria for withdrawal of subjects from the study, the investigators shall follow the following procedures.

- The date of discontinuation (the date on which discontinuation was judged and the date of last dose, if possible) and the reason for discontinuation, as well as comments on discontinuation if necessary, will be entered in the eCRF.

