##### **2.1.1.2 Efficacy analysis set**

Of any assigned patients, any patients excluding those who did not receive the study drug or those from whom no information on efficacy was available after allocation are defined as the Full Analysis Set (FAS). In this study, an analysis will be performed in the FAS. In addition, any patients in the FAS excluding those with major protocol violations after start of treatment and for whom the efficacy is evaluable are defined as the Per Protocol Set (PPS). Analysis of the primary endpoint will be performed in the PPS.

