2) For patients who were categorized in each category on a 7-point ordinal scale on Day 14 (or at the last observation the point) and Day 28 (or at the last observation time point between Day 15 and Day 27), the p-values (Wilcoxon's rank sum test) of the differences between groups will be calculated.

2.1.2.10.2.9 Distribution and proportion of patients in each category of oxygen requirement until Day14

(1) Analysis set : FAS

(2) Analysis item : oxygen requirement

(3) Time point : Day 0 to Day 14

(4) Analytical method :

1) The number of patients and the proportion in each category on the oxygen requirement shown in Table 2.2 until Day 14 will be summarize by treatment group and by time point (number of patients, %). In addition, a bar chart showing the percentage of each category will be prepared by treatment group and by time point.

2) For patients who were categorized in each category on the oxygen requirement on Day 5 and Day 14, the p-values (Wilcoxon's rank sum test) of the differences between groups will be calculated.

Table 2.2 Oxygen requirement

Category	Ordinal scale
1	Require oxygen supply of 4 L/min or more using oxygen mask
2	Require oxygen supply of 2 L/min or more using nasal cannulas
3	Require oxygen supply of less than 2 L/min using nasal cannulas
4	Do not require oxygen supply but feel shortness of breath during walking or moving
5	Do not require oxygen supply and do not feel shortness of breath during walking or moving

Table 2.3 Definition of event/censoring in Time to event analysis

Analysis item	Event/ Censoring	Definition of event/censoring	Period

 
Period to the first improvement by at least 2-rank between baseline and Day 28 on a 7-point ordinal scale 
 
Period from baseline to the day of discharge
 
Period from baseline to shifting to Category 6 or 7 on a 7-point ordinal scale
 
Period from baseline to shifting to Category 5 on a 7-point ordinal scale
 
Period to from baseline to improvement by 1 rank or more on a 7-point ordinal scale
 
 
 
	Event	A patient who developed an event	Period until the onset of the first event
	Censoring	A patient who completed the study without any event	Period until the last observation day
		A patient who discontinued or died	Censored after complementing 29 days*

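### Patients found ineligible after the start must leave the study, so an outcome that could still be observed goes uncollected and SAP Table 2.3 counts them as non-improvers through Day 28

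*Protocol*

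**What the plan says.** Protocol 15.2 is mandatory: "A subject who meets any of the following criteria shall be withdrawn from study participation". Criterion (1) is that "The subject was found not to meet the inclusion criteria or to meet the exclusion criteria and to be ineligible for the clinical study", judged on examinations done after the start, with no time limit. What must then be recorded is "The date of discontinuation (the date on which discontinuation was judged and the date of last dose, if possible) and the reason for discontinuation", plus comments if needed. Nothing further on the ordinal scale is requested.

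Protocol 15.1 deals with stopping study drug. There "a policy was decided to follow-up and to collect the data on Japanese COVID-19 patients who participated in the clinical study whenever possible", but scheduled procedures continue only if no 15.2 criterion is met. Ineligibility is not among the 15.1 criteria, so the protocol offers no route by which such a patient stops the drug and stays under observation.

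The FAS in SAP 2.1.1.2 is "any patients excluding those who did not receive the study drug" or who have no efficacy information after allocation. It has no exclusion for ineligibility. The PPS removes major violations, but only those arising after treatment has started.

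SAP Table 2.3 governs the primary endpoint. A patient with an event is counted at the first event. Among those without one, "A patient who discontinued or died" is "Censored after complementing 29 days", whatever the reason for leaving. The footnote explains this by patients who stop early because they worsened, whose loss would make the improvement rate look too high.

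**The concern.** The ordinal scale is already scheduled daily to Day 28, including after discharge. A patient removed for an eligibility finding has not thereby worsened, and improvement or discharge could still be observed. The plan leaves that outcome uncollected and puts an assumed failure in its place in the primary analysis. This departs from the aim stated in 15.1 and from complete follow-up of randomised patients.

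The loss also need not be random with respect to outcome. Exclusion (14) is investigator judgement, and exclusion (8), earlier lung disease that may affect assessment, needs judgement too. Both can be re-judged once the clinical course is visible. With about 20 controls, each such patient carries weight.

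**Working it through.** **Inputs from the documents.** 40 active and 20 control; normal event times with means 10 and 14 days and common SD 4.5; log-rank test at two-sided 5%; stated power 82.1% (protocol sections 17.5 and 18). Follow-up ends at Day 28 (SAP 2.1.2.10.1).

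**Assumed, because the documents give no figure.** The number withdrawn for ineligibility in each arm, and a withdrawal day drawn at random from Days 1 to 5. An improvement before withdrawal is kept as an event.

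**Step 1: reproduce the planned power.** Simulating the stated model with administrative censoring at Day 28 gives 82.7% (5,000 runs), or 83.7% with event times rounded up to whole days (3,000 runs). The stated 82.1% is reproduced.

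**Step 2: what a 29-day censoring time does.** No event can fall after Day 28, so a patient censored at 29 is in every risk set and never improves. Each such patient who would have improved lowers the Day 28 improvement rate by 1/40 = 2.5 points (active) or 1/20 = 5 points (control). The log-rank effect is larger than those figures suggest. In the planning model active patients improve early, which builds an excess of observed over expected active events. Two active patients held at risk keep adding expected active events with none observed: with 4 controls left, a control event adds 2/(2+4) = 0.33. That erodes the excess. Held controls push the other way.

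**Step 3: power under three treatments of the same withdrawals** (3,000 runs each, continuous time, Monte Carlo error about 1 point).

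| Withdrawn, active + control | Follow-up continued to Day 28 | Censored at withdrawal | Table 2.3 (29 days) |
|---|---|---|---|
| 1 + 1 | 81.8% | 80.5% | 78.9% |
| 2 + 1 | 81.5% | 79.9% | 57.2% |
| 4 + 2 | 81.7% | 78.7% | 34.6% |
| 6 + 3 | 82.1% | 75.8% | 17.3% |

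For 2 + 1 the total loss is 81.5 - 57.2 = 24.3 points. Lost follow-up alone costs 81.5 - 79.9 = 1.6 points; the 29-day value costs the other 79.9 - 57.2 = 22.7. Across repeated runs, with continuous or whole-day times, the Table 2.3 result for 2 + 1 lies between about 57% and 62%.

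**Step 4: other event-time models, 2 + 1 withdrawn.** With 10% true non-improvers in both arms, power goes from about 38% to 27%. With exponential times it goes from about 19% to 15%. Starting power is lower and the absolute loss is smaller.

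**Step 5: no true effect (both means 14).** If each patient is withdrawn independently of arm, the rejection rate is 5.0%, 5.2%, 5.8% and 5.0% at withdrawal rates of 2%, 5%, 7% and 10% (2,500 runs each, Monte Carlo error about 0.4 points). With fixed counts it depends on which arm loses patients:
- 2 active + 1 control: about 1%
- 1 active + 3 control: about 13-16%
- 3 active only: 10.9%
- 3 control only: 31.2%

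**The case against.** Three stronger readings are tempting, and the documents do not support them.

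- **That 15.2(1) contradicts 15.1.** Section 15.1 expressly gives way to 15.2, and its follow-up policy is qualified by what is possible. The two are consistent as written. What remains is a departure from the aim, not a conflict of rules.
- **That a patient who has improved or gone home is overwritten as a failure.** Table 2.3 counts an event first. Improvement or discharge before withdrawal stands; only what would have happened afterwards is lost. Those outcomes are uncollected, not known and then replaced.
- **That the rule inflates type I error.** The trial is double-blind and the documents give no mechanism for eligibility findings to depend on arm. Step 5 gives about 5% under arm-independent withdrawal, and a conservative test for 2 + 1. The inflated figures need an imbalance chosen in advance or arising by chance.

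Other points have weight. Eligibility is checked at screening and again on Day 0 before randomisation (protocol 10.1), so cases may be few. Criterion (1) has a stated rationale of safety and proper evaluation. The Case Review Committee may rule on set membership in difficult cases (SAP 2.1.1). But that is discretion over analysis sets, not a rule for ineligible patients, and it cannot recover assessments never made. Most of the numerical harm does belong to the Day 29 rule, which needs attention in its own right. That limits the size attributable to 15.2(1) alone, but the two provisions act together on these patients.

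**Conclusion.** The concern holds as a correctable weakness of design. The protocol stops observing a treated patient for a reason unconnected with worsening, the FAS normally retains that patient, and Table 2.3 supplies a failure for which its own footnote gives no ground.

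Under the planning model and an assumed 2 + 1 withdrawal on Days 1-5, power drops from about 82-84% to about 57-62%, against about 80-82% with censoring at withdrawal. This is an illustration, not a forecast. The counts and timing are assumptions, and the drop is as large as it is because practically everyone improves by Day 28 in the planning model. Type I error is not a general problem here; it rises only if withdrawals happen to concentrate in one arm.

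**What to change.** - **Protocol 15.2(1).** State that ineligibility found after randomisation does not end ordinal-scale follow-up to Day 28 unless consent is withdrawn. Handling of study drug for these patients stays with the sponsor and the investigator.
- **SAP 2.1.2.10.1.** Analyse the observed outcome of these patients in the FAS.
- **SAP 2.1.1.2.** Extend the PPS exclusion to eligibility violations. It is now limited to major violations after treatment has started, so the PPS cannot be relied on to remove patients who were ineligible at entry.
- **SAP Table 2.3.** Do not apply the 29-day value to withdrawals for ineligibility. Where follow-up has nonetheless ended, censor at the last ordinal-scale assessment. Align this with any wider revision of the Day 29 rule.

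The cost is wording in two documents, and a few patients remaining in the daily status follow-up already planned for everyone. In the planning model, continued follow-up keeps power at the planned level (81.5-82.1% in the table above).
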